8.3 Definition of Visit Windows

Table 3 of the protocol presents the schedule of procedures/Assessments. The screening/baseline period is four weeks long and procedures/assessments are performed at randomization, weeks 1, 2, 4, 6, 10, and 14 of the treatment period with a follow-up of 4 weeks after end of treatment. Table 3 presents the protocol specified visits/weeks and corresponding time windows used for visit-wise analyses are presented in terms of days relative to the randomization. If more than one measurement is included in a visit window, the measurement collected closest to the scheduled date will be used in the analysis. In the case where two measurements were collected an equal number of days before and after the Scheduled Day the later of the two measurements will be used for analysis. For ECHO assessments when assessing a new or worsened event then the most severe assessment will be selected if 2 or more assessments fall within a visit window

Eisai Final 4.0 Confidential Page 23 of 30

Table 3 Visit Windows Measurements

Scheduled	Scheduled Week	Scheduled	Time Window (Days)	
1	Screening		First day of Screening	-1
2	Baseline/ Randomization	1	1	
3	1	7	2	10
4	2	14	11	17
5	4	28	18	34
6	6	42	35	48
7	10	70	49	82
8	14	98	83	101
Extension Phase				
9	15	105	102	110
10	17	119	111	125
11	20	140	126	149
12	23	161	150	169
13	26	182	170	194

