9.5.2 Schedule of Procedures/Assessments

9.5.2.1 Schedule of Procedures/Assessments

[Table 3](#) presents the Schedule of Procedures/Assessments for the Core Study.

Table 3 Schedule of Procedures/Assessments in Study E2023-A001-304: Core Study

Phase	Prerandomization	Randomization									
Period	Screening/Baseline	Treatment ^a							Follow-up ^{b,c}		
Visit	1	2	3	4	5	6	7	8		ED ^d	Unscheduled ^e
Week	From -4 Weeks to Week 0	0	1	2	4	6	10	14	4 weeks after the last dose		
Procedures/Assessments											
Demography	X										
Informed consent/assent	X										
Inclusion/exclusion criteria	X	X									
Medical history	X										
Epilepsy history ^f	X										
Prior and concomitant medications	X	X	X	X	X	X	X	X	X	X	X
Prior and concomitant AEDs	X	X	X	X	X	X	X	X	X	X	X
Adverse events	X	X	X	X	X	X	X	X	X	X	X
Randomization		X									
Study drug compliance			X	X	X	X	X	X		X	X ^{e,g}
Dispense study drug		X	X	X	X	X	X	X ^h			X ^{e,g}
Retrieve unused study drug			X	X	X	X	X	X		X	X ^{e,g}
Dispense subject's diary	X	X	X	X	X	X	X	X ^h			X ^e
Retrieve and review diary		X	X	X	X	X	X	X		X	X ^e
Neurological examination ⁱ	X							X		X	

Table 3 Schedule of Procedures/Assessments in Study E2023-A001-304: Core Study

Phase	Prerandomization	Randomization									
Period	Screening/Baseline	Treatment ^a							Follow-up ^{b,c}		
Visit	1	2	3	4	5	6	7	8		ED ^d	Unscheduled ^e
Week	From -4 Weeks to Week 0	0	1	2	4	6	10	14	4 weeks after the last dose		
Procedures/Assessments											
Physical examination ⁱ	X							X		X	
Vital signs, and weight	X	X	X	X	X	X	X	X		X	X ^e
Height	X										
Clinical laboratory tests ^j	X					X		X		X	X ^{e,k}
Serum β-hCG test ^l	X										
Urine pregnancy test ^l		X						X		X	X ^e
12-Lead ECG ^m	X							X		X	X ^{e,k}
Echocardiogram	X							X		X	X ^{e,k}
PK sampling (plasma) ⁿ			X	X	X	X				X ^o	
IxRS call	X	X	X	X	X	X	X	X		X	X ^e
C-SSRS	X	X	X	X	X	X	X	X		X	
QoL		X						X		X	
Clinical Global Impression ^p		X						X		X	

AE = adverse event, AED = antiepileptic drug, β-hCG = beta-human chorionic gonadotropin, COVID-19 = Coronavirus disease 2019,

C-SSRS = Columbia-Suicide Severity Rating Scale, ECG = electrocardiogram, ED = early discontinuation, IxRS = interactive voice and web response system,

Table 3 Schedule of Procedures/Assessments in Study E2023-A001-304: Core Study

Phase	Prerandomization	Randomization									
Period	Screening/Baseline	Treatment ^a							Follow-up ^{b,c}		
Visit	1	2	3	4	5	6	7	8		ED ^d	Unscheduled ^e

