Week	From -4 Weeks to Week 0	0	1	2	4	6	10	14	4 weeks after the last dose		
Procedures/Assessments											

PedsQL = Pediatric Quality of Life Inventory, PK = pharmacokinetic, QoL = Quality of Life in Epilepsy Scale/Pediatric Quality of Life Inventory 4.0; QOLIE-31 = Quality of Life in Epilepsy Survey.

- a: All visits to be done within ± 3 days of the schedule. If any of the visits after Visit 1 are conducted remotely due to the COVID-19 pandemic, at a minimum, the following assessments should be conducted: AEs, suicidality assessment, concomitant medications, review of seizure diary data, and study drug compliance (any missed or extra doses with dates). Study drug and seizure diary may be picked up from the site by the subject/caregiver or shipped from the site to the subject's location. C-SSRS and Clinical Global Impression may be conducted remotely over the phone by a qualified rater and QOLIE-31 and PedsQL based on input from subject over the phone.
- b: Visit to be done within ± 7 days of the schedule.
- c: The Follow-up Visit only applies to those subjects who do not enter the Extension Phase after completion of this study.
- d: These assessments will be conducted for subjects who discontinue the study or treatment early for any reason after Visit 2.
- e: At Unscheduled Visits these assessments/procedures conducted if needed.
- f: Epilepsy history will include information on genetic mutation related to epilepsy, if available.
- g: Unused study drug to be retrieved and study drug dispensed only for subjects requiring dose change at Unscheduled Visits.
- h: Study drug and seizure diary will be dispensed only for subjects who enter the Extension Phase.
- i: Physical and neurological examinations will only be performed at the indicated visits. For all other clinic visits during the study, the physical and the neurological examinations will only be performed when there is a complaint from the subject. Clinically significant abnormal findings from the physical or the neurological examinations will be reported as AEs.
- j: Clinical laboratory tests include hematology, blood chemistry, and urinalysis.
- k: At Unscheduled Visits, these assessments will only be done if the results from the previous visit were deemed clinically significant by the investigator.
- l: Only for female subjects of child-bearing potential (defined as all postmenarche females, unless postmenopausal or have been sterilized surgically).

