3.2 Overall Study Design and Plan

This is a multicenter, multiple-dose, randomized, double-blind, placebo-controlled, parallel-group adjunctive therapy study in subjects with Dravet syndrome. The study is planned to be conducted in US, Canada, India, and China or Brazil (to be determined). The study will consist of a Core Study and open-label Extension Phase.

The Core Study will include a Prerandomization and a Randomization Phase.

The Prerandomization Phase will include a Screening/Baseline Period (4 weeks), during which the subjects will be assessed for eligibility.

Once the Screening and Baseline procedures have been completed and eligibility has been established, the subjects will be randomized and begin treatment in the Randomization Phase. Approximately 62 subjects will be randomized to 1 of 2 treatment groups in a ratio of 1:1 and will receive lorcaserin or placebo for 14 weeks. The randomization will be centralized and stratified by previous treatment with fenfluramine (yes, no) and by weight categories (10 to <20 kg, 20 to <40 kg, and ≥40 kg). The stratification factors will be balanced between treatment groups using restricted randomization method proposed by Pocock and Simon (1975).

The Randomization Phase will consist of 2 periods: Treatment Period (14 weeks) and Follow-up Period (4 weeks).

During the Treatment Period, all subjects will take study drug twice daily (BID) based on weight category at randomization, as described in Section 9.4.1 of the protocol.

For lower weight categories, during the first 2 weeks of Treatment Period, the dose may be increased (not earlier than after 1 week of treatment) by 1 dose level at a visit. If the dose was increased, in the event of AEs, according to the investigator's clinical judgment, the dose may remain the same or can be decreased by 1 dose level, to the Target dose at any time during the Treatment Period. If the dose had been decreased, it may be increased again if tolerability improves.

All subjects who complete the Core Study will be eligible to enter the Extension Phase (refer to Appendix 2 of the protocol). The last visit of the Treatment Period of the Core Study is considered to be the 1st visit of the Extension Phase.

The Follow-up Visit will be conducted 4 weeks after the last dose of study drug for subjects who do not enter the Extension Phase.

Eisai Final 4.0 Confidential Page 9 of 30

dose

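### SAP Table 3 sets visit days one day earlier than its own Day 1 origin implies, so a Visit 8 on the protocol's last allowed day (Day 102) is filed under Extension Week 15

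*SAP*

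**What the plan says.** SAP Section 8.3 assigns measurements to visits by study day: the "corresponding time windows used for visit-wise analyses are presented in terms of days relative to the randomization". In SAP Table 3 the screening window closes at Day -1 and the next row reads "Baseline/ Randomization 1 1", so there is no Day 0. Visit 8 (Week 14) is scheduled for Day 98 with a window of Days 83 to 101. The first Extension row follows directly: "9 15 105 102 110" (visit, week, scheduled day, window start, window end). When a window holds more than one measurement, "the measurement collected closest to the scheduled date will be used in the analysis"; a tie goes to the later one. For echocardiograms assessed for a new or worsened event, the most severe is taken. Section 8.3 gives no priority to the nominal visit or to study phase.

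The week row of Protocol Table 3 (Section 9.5.2.1) reads "From -4 Weeks to Week 0 0 1 2 4 6 10 14", so Visit 2 is Week 0 and Visit 8 is Week 14. Footnote a sets the tolerance: "All visits to be done within ± 3 days of the schedule". On the link between phases, SAP Section 3.2 says: "The last visit of the Treatment Period of the Core Study is considered to be the 1st visit of the Extension Phase". Visit 9 is a separate visit at Week 15.

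**The concern.** The table mixes two day counts. Its origin is Day 1, but its scheduled days are those of a count that starts at Day 0. The one-day gap costs nothing where windows are wide. It matters where a window's upper limit is the scheduled day plus exactly three, because the protocol's last allowed day then falls into the next window.

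At Visits 3 and 4 the result moves to a neighbouring Core visit. At Visit 8 it crosses from Core to Extension. Visit 8 is the only scheduled Core treatment visit with an ECG or an echocardiogram, and one of two with laboratory tests (the other is Visit 6). SAP Sections 5.6.3 to 5.6.5 report laboratory values, vital signs, ECG parameters and new FDA-defined valvulopathy by visit and treatment group. A subject seen on time under the protocol could therefore be missing from those Week 14 tables.

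**Working it through.** **Inputs.** Scheduled days and windows: SAP Table 3. Visit weeks and the ±3-day tolerance: Protocol Table 3 and, for Visits 9 to 13, Protocol Table 4. Number randomized: SAP Section 7.

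**Step 1: reproduce the SAP's scheduled days.** 7 × week gives 7, 14, 28, 42, 70, 98, 105, 119, 140, 161 and 182, which are all 11 post-randomization entries. This is the day number only if randomization is Day 0.

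**Step 2: apply the table's own origin.** With randomization at Day 1 and no Day 0, a visit w weeks later falls on Day 7w + 1. The compliant range is 7w + 1 ± 3.

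| Visit | Week | SAP day (7w) | 7w + 1 | Compliant range | SAP window | Last allowed day goes to |
|---|---|---|---|---|---|---|
| 3 | 1 | 7 | 8 | 5–11 | 2–10 | **Visit 4** |
| 4 | 2 | 14 | 15 | 12–18 | 11–17 | **Visit 5** |
| 5 | 4 | 28 | 29 | 26–32 | 18–34 | Visit 5 |
| 6 | 6 | 42 | 43 | 40–46 | 35–48 | Visit 6 |
| 7 | 10 | 70 | 71 | 68–74 | 49–82 | Visit 7 |
| 8 | 14 | 98 | 99 | 96–102 | 83–101 | **Visit 9 (Extension)** |
| 9 | 15 | 105 | 106 | 103–109 | 102–110 | Visit 9 |
| 10 | 17 | 119 | 120 | 117–123 | 111–125 | Visit 10 |
| 11 | 20 | 140 | 141 | 138–144 | 126–149 | Visit 11 |
| 12 | 23 | 161 | 162 | 159–165 | 150–169 | Visit 12 |
| 13 | 26 | 182 | 183 | 180–186 | 170–194 | Visit 13 |

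There are three mismatches, all at +3 days. Every compliant early visit stays in its own window.

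**Step 3: what happens to a Day 102 Visit 8.** Protocol Table 4 schedules laboratory tests and ECG only at Visit 13 or early discontinuation (unscheduled visits aside), and no echocardiogram at all. Those Day 102 results would be absent at Week 14 and appear at Week 15, where none is planned. Vital signs are taken at Visit 9 as well. An on-time Visit 9 on Day 106 is 106 − 105 = 1 day from the SAP's scheduled day, against 105 − 102 = 3 days for the Day 102 record. The closest-date rule keeps Visit 9, and the Week 14 vital signs appear in neither row.

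**Step 4: size per subject.** SAP Section 7 reports 22 randomized. At 1:1 that is about 22 / 2 = 11 per arm, so one misfiled subject is 1 / 11 = 9% of an arm.

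**Step 5: check the repair.** Upper limits of 11, 18 and 102, with the next windows opening at 12, 19 and 103, contain Visit 3 (5–11), Visit 4 (12–18), Visit 8 (96–102) and Visit 9 (103–109). Visit 5 (26–32) still fits its window, now 19–34.

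**The case against.** The best defence is that the table follows a deliberate convention. The protocol states weeks, not day numbers. The imputation code in SAP Section 9 runs the double-blind phase from day 1 to day 98, an inclusive count of 14 weeks. The three tight limits are exactly the scheduled day plus three: 7 to 10, 14 to 17, 98 to 101. If ±3 is anchored to Day 98, the last allowed day is Day 101 and nothing is misfiled. That explains how the table arose. It does not match the protocol, in which Visit 8 is 14 weeks after Week 0: Day 98 in the Day 1 count is 97 days after randomization, or 13 weeks and 6 days.

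The defence is right about reach. Primary, key secondary and seizure-freedom results are computed over the whole Treatment Period (SAP Section 8.1). The multiple imputation does sum seizures by visit window, but SAP Section 7 drops sensitivity analyses. The laboratory last-on-treatment value and overall incidence summaries do not depend on a visit label.

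A reader might infer further harms that the documents do not support:

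- **Lost C-SSRS, quality-of-life, examination or CGIC results.** The SAP states no by-visit analysis for the first three, and its text on CGIC analysis is not visible.
- **Placebo results reported as lorcaserin data.** The SAP does not say how Extension tables label former placebo subjects, and derivation rules sit in separate documents.
- **Extension readings entering Core Week 14.** Nothing is scheduled between Visits 8 and 9, so this would need an unscheduled assessment.
- **A rate of one in seven (14%), or about 1.6 of 11 per arm.** That assumes visits spread evenly over the seven allowed days and that all 22 subjects reached Visit 8. The documents give no visit-timing data.

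**Conclusion.** The inconsistency is real and remains relevant after termination, because SAP Section 7 curtails efficacy, subgroup, sensitivity and PK work but does not withdraw the by-visit safety tables. It rests on reading Week 14 as 14 full weeks after Week 0 and on the SAP as written, which has no nominal-visit or phase override. The unseen programming specifications might contain one.

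The exposure is one calendar day at each of three visits, with a consequence of note only at Visit 8. The number of subjects affected is unknown and could be zero; each would be about 9% of an arm, assuming a near-even split of the 22. Severity is minor: a correction to the Week 14 laboratory, vital-sign, ECG and new-valvulopathy tables, with no effect on the efficacy conclusions.

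**What to change.** In SAP Table 3:

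- Extend the upper limits to Day 11 (Visit 3), Day 18 (Visit 4) and Day 102 (Visit 8), and start the windows for Visits 4, 5 and 9 at Days 12, 19 and 103.
- Set scheduled days at 7 × week + 1 (8, 15, 29, 43, 71, 99, 106, 120, 141, 162, 183), so that closest-date selection uses the same origin. The boundary changes alone cure the three misfilings. Re-basing can change which of two measurements is chosen at other visits, so it should be stated openly.
- Add to Section 8.3 that assessments up to and including Visit 8, made before the first Extension dose, are Core, and later ones are Extension, whatever the day window. A subject with no Extension dose stays in Core.

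The cost is a table edit and a short programming rule, with no new data. Protocol Section 9.7.5 already provides for describing such a revision in the clinical study report.

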9 PROGRAMMING SPECIFICATIONS

The rules for programming derivations and dataset specifications are provided in separate documents.

The following SAS pseudo code is to outline the algorithm for using multiple imputation methodology under missing not at random (MNAR) assumption for imputing missing data for the primary endpoint seizure frequency, during the double-blind period.

The following covariates will be used in the imputation models.

Step 1: Impute arbitrary missing days and create dataset into monotone missing patterns

PROC MI data=<dataset> nimpute=30 seed=2023 out=<dataset1>; MCMC chain=multiple nbiter=500 niter=300 impute=monotone; VAR age weight log(day1) - log(day98 or last day of double-blind phase); BY treatment; RUN;

Eisai Final 4.0 Confidential Page 24 of 30

- Exponentiation of log transformed data
- Generate visit windows visit 1 to visit 8
- Determined the sum of seizures per visit window.
- Log transformed sum of seizures per visit window.

Step 2: Impute missing values assuming MNAR

```
PROC MI data=<dataset1> nimpute=1 seed=2023 out=<dataset2>; CLASS treatment sex race; MONOTONE regpmm (/details k=5); MNAR model (visit1-visit8/ modelobs=CCMV(k=8)); VAR treatment fenfluramine_strata weight_strata sex race age region log(visit1) - log(visit8); BY _imputation_; RUN;
```

Step 3:

For each imputed dataset;

- Exponentiation of log transformed data
- Derived the Baseline and Treatment Period seizure frequency per 28 days
- Derived percent change from baseline
- Rank baseline period seizure frequency per 28 days
- Rank percent change change from baseline in seizure frequency per 28 days

PERFORMING ANALYSIS FOR EACH IMPUTED DATASET:

```
PROC MIXED data=<dataset2>;
CLASS treatment(ref='placebo') fenfluramine_strata weight_strata;
MODEL rank_value=baseline_rank treatment fenfluramine_strata weight_strata region;
LSMEANS treatment/diff;
BY _imputation_;
ODS OUTPUT Diffs=<dataset3>;
RUN;
```

COMBINE RESULTS:

```
PROC MIANALYZE data=<dataset3>;
MODELEFFECTS estimate;
STDERR stderr;
ODS OUPUT PARAMETERESTIMATES= <dataset4>;
RUN;
```

Eisai Final 4.0 Confidential Page 25 of 30

10 STATISTICAL SOFTWARE

All statistical analyses will be performed using SAS v 9.4 or later.

11 MOCK TABLES, LISTINGS, AND GRAPHS

The study TLG shells will be provided in a separate document, which will show the content and format of all tables, listings, and graphs in detail.

13 APPENDICES

13.1 Sponsor's Grading for Determining Markedly Abnormal Laboratory Results

The following table of Sponsor's Grading for Laboratory Values is copied from the protocol, Appendix 1,

Sponsor's Grading for Laboratory Values

	Grade 1	Grade 2	Grade 3	Grade 4			
BLOOD/BONE MARROW	BLOOD/BONE MARROW						
Hemoglobin	<lln -="" 10.0="" dl
<lln -="" 100="" g="" l
<lln -="" 6.2="" l<="" mmol="" td=""><10.0 – 8.0 g/dL <100 – 80 g/L <6.2 – 4.9 mmol/L	<8.0 g/dL <80 g/L <4.9 mmol/L; transfusion indicated	Life-threatening consequences; urgent intervention indicated	</lln></lln></lln>	<10.0 – 8.0 g/dL <100 – 80 g/L <6.2 – 4.9 mmol/L	<8.0 g/dL <80 g/L <4.9 mmol/L; transfusion indicated	Life-threatening consequences; urgent intervention indicated			
Leukocytes (total WBC)	<lln -="" 3.0×109/L <lln -="" 3000="" mm3</lln></lln>	<3.0 - 2.0×10 ⁹ /L <3000 - 2000/mm ³	<2.0 - 1.0×10 ⁹ /L <2000 - 1000/mm ³	<1.0×10 ⁹ /L <1000/mm ³			
Lymphocytes	<lln -="" 800="" mm3 <lln -="" 0.8×109/L</lln></lln>	<800 - 500/mm ³ <0.8 - 0.5×10 ⁹ /L	<500 - 200/mm ³ <0.5 - 0.2×10 ⁹ /L	<200/mm ³ <0.2×10 ⁹ /L			
Neutrophils	<lln -="" 1.5×109/L <lln -="" 1500="" mm3</lln></lln>	<1.5 - 1.0×10 ⁹ /L <1500 - 1000/mm ³	<1.0 - 0.5×10 ⁹ /L <1000 - 500/mm ³	<0.5×10 ⁹ /L <500/mm ³			
Platelets	<lln -="" 75.0×109/L <lln -="" 75,000="" mm3</lln></lln>	<75.0 - 50.0×10 ⁹ /L <75,000 - 50,000/mm ³	<50.0 - 25.0×10 ⁹ /L <50,000 - 25,000/mm ³	<25.0×10 ⁹ /L <25,000/mm ³			
METABOLIC/LABORATORY							
Albumin, serum – low (hypoalbuminemia)	<lln -="" 3="" dl
<lln -="" 30="" g="" l<="" td=""><3 - 2 g/dL <30 - 20 g/L	<2 g/dL <20 g/L	life-threatening consequences; urgent intervention indicated	</lln></lln>	<3 - 2 g/dL <30 - 20 g/L	<2 g/dL <20 g/L	life-threatening consequences; urgent intervention indicated			

Eisai Final 4.0 Confidential Page 27 of 30

Sponsor's Grading for Laboratory Values

	Grade 1	Grade 2	Grade 3	Grade 4
Alkaline phosphatase	>ULN – 2.5×ULN if baseline was normal; 2.0 – 2.5×baseline if baseline was abnormal	>2.5 – 5.0×ULN if baseline was normal; >2.5 – 5.0×baseline if baseline was abnormal	>5.0 – 20.0×ULN if baseline was normal; >5.0 – 20.0×baseline if baseline was abnormal	>20.0×ULN if baseline was normal; >20.0×baseline if baseline was abnormal
ALT	>ULN – 3.0×ULN if baseline was normal; 1.5 – 3.0×baseline if baseline was abnormal	>3.0 – 5.0×ULN if baseline was normal; 3.0 – 5.0×baseline if baseline was abnormal	>5.0 – 20.0×ULN if baseline was normal; >5.0 – 20.0×baseline if baseline was abnormal	>20.0×ULN if baseline was normal; >20.0×baseline if baseline was abnormal
AST	>ULN – 3.0×ULN if baseline was normal; 1.5 – 3.0×baseline if baseline was abnormal	>3.0 – 5.0×ULN if baseline was normal; 3.0 – 5.0×baseline if baseline was abnormal	>5.0 – 20.0×ULN if baseline was normal; >5.0 – 20.0×baseline if baseline was abnormal	>20.0×ULN if baseline was normal; >20.0×baseline if baseline was abnormal
Bilirubin (hyperbilirubinemia)	>ULN – 1.5×ULN if baseline was normal; 1.0 – 1.5×baseline if baseline was abnormal	>1.5 – 3.0×ULN if baseline was normal; 1.5 – 3.0×baseline if baseline was abnormal	>3.0 – 10.0×ULN if baseline was normal; 3.0 – 10.0×baseline if baseline was abnormal	>10.0×ULN if baseline was normal; >10.0×baseline if baseline was abnormal
Calcium, serum-low (hypocalcemia)	<lln -="" 8.0="" dl
<lln -="" 2.0="" l
Ionized calcium <lln -="" 1.0="" l<="" mmol="" td=""><8.0 – 7.0 mg/dL <2.0 – 1.75 mmol/L Ionized calcium <1.0 – 0.9 mmol/L; symptomatic	<7.0 – 6.0 mg/dL <1.75 – 1.5 mmol/L Ionized calcium <0.9 – 0.8 mmol/L; hospitalization indicated	<6.0 mg/dL <1.5 mmol/L Ionized calcium <0.8 mmol/L; life-threatening consequences	</lln></lln></lln>	<8.0 – 7.0 mg/dL <2.0 – 1.75 mmol/L Ionized calcium <1.0 – 0.9 mmol/L; symptomatic	<7.0 – 6.0 mg/dL <1.75 – 1.5 mmol/L Ionized calcium <0.9 – 0.8 mmol/L; hospitalization indicated	<6.0 mg/dL <1.5 mmol/L Ionized calcium <0.8 mmol/L; life-threatening consequences
Calcium, serum-high (hypercalcemia)	>ULN – 11.5 mg/dL >ULN – 2.9 mmol/L Ionized calcium >ULN – 1.5 mmol/L	>11.5 – 12.5 mg/dL >2.9 – 3.1 mmol/L Ionized calcium >1.5 – 1.6 mmol/L; symptomatic	>12.5 – 13.5 mg/dL >3.1 – 3.4 mmol/L Ionized calcium >1.6 – 1.8 mmol/L; hospitalization indicated	>13.5 mg/dL >3.4 mmol/L Ionized calcium >1.8 mmol/L; life-threatening consequences
Cholesterol, serum-high (hypercholesterolemia)	>ULN - 300 mg/dL >ULN - 7.75 mmol/L	>300 – 400 mg/dL >7.75 – 10.34 mmol/L	>400 – 500 mg/dL >10.34 – 12.92 mmol/L	>500 mg/dL >12.92 mmol/L
Creatinine	>ULN – 1.5×ULN	>1.5 – 3.0×baseline; >1.5 – 3.0×ULN	>3.0×baseline; >3.0 – 6.0×ULN	>6.0×ULN
GGT (γ-glutamyl transpeptidase)	>ULN – 2.5×ULN if baseline was normal; 2.0 – 2.5×baseline if baseline was abnormal	>2.5 – 5.0×ULN if baseline was normal; >2.5 – 5.0×baseline if baseline was abnormal	>5.0 – 20.0×ULN if baseline was normal; >5.0 – 20.0×baseline if baseline was abnormal	>20.0×ULN if baseline was normal; >20.0× baseline if baseline was abnormal
Glucose, serum-high (hyperglycemia)	Abnormal glucose above baseline with no medical intervention	Change in daily management from baseline for a diabetic; oral antiglycemic agent initiated; workup for diabetes	Insulin therapy initiated; hospitalization indicated	life-threatening consequences; urgent intervention indicated

Eisai Final 4.0 Confidential Page 28 of 30 May 18, 2024

Sponsor's Grading for Laboratory Values

	Grade 1	Grade 2	Grade 3	Grade 4
Glucose, serum-low (hypoglycemia)	<lln -="" 55="" dl
<lln -="" 3.0="" l<="" mmol="" td=""><55 – 40 mg/dL <3.0 – 2.2 mmol/L	<40 – 30 mg/dL <2.2 – 1.7 mmol/L	<30 mg/dL <1.7 mmol/L; life-threatening consequences; seizures	</lln></lln>	<55 – 40 mg/dL <3.0 – 2.2 mmol/L	<40 – 30 mg/dL <2.2 – 1.7 mmol/L	<30 mg/dL <1.7 mmol/L; life-threatening consequences; seizures
Phosphate, serum-low (hypophosphatemia)	Laboratory finding only and intervention not indicated	Oral replacement therapy indicated	Severe or medically significant but not immediately life- threatening; hospitalization or prolongation of existing hospitalization indicated	life-threatening consequences
Potassium, serum-high (hyperkalemia)	>ULN – 5.5 mmol/L	>5.5 – 6.0 mmol/L	>6.0 – 7.0 mmol/L hospitalization indicated	>7.0 mmol/L life-threatening consequences
Potassium, serum-low (hypokalemia)	<lln 3.0="" l<="" mmol="" td="" –=""><lln 3.0="" l;
symptomatic; intervention indicated</lln>	<3.0 – 2.5 mmol/L hospitalization indicated	<2.5 mmol/L life-threatening consequences	</lln>	<lln 3.0="" l;
symptomatic; intervention indicated</lln>	<3.0 – 2.5 mmol/L hospitalization indicated	<2.5 mmol/L life-threatening consequences
Sodium, serum-high (hypernatremia)	>ULN - 150 mmol/L	>150 – 155 mmol/L; intervention initiated	>155 – 160 mmol/L hospitalization indicated	>160 mmol/L life-threatening consequences
